**Table 3.7.3-2 Sparse Sampling Schedule Trial Days and Activities**

| Days 36, 43, and 50 ± 2 days (outpatient, subjects receiving aripiprazole 2M LAI 960 mg)   |  |
|---|--|
| 
 
• Document birth control methods.
 
• Record concomitant medications and review for prohibited or restricted medications.
 
• Record adjustment of current oral antipsychotic, mood stabilizer, or antidepressant therapy.
 
• Assess and record AEs.
 
• Take vital signs (systolic and diastolic blood pressure, heart rate, and body temperature).
 
• Administer the Since Last Visit version of the C-SSRS.
 
• Draw a PK blood sample between 8 AM and 2 PM.
 
  |  |
| Day 57 ± 2 days (outpatient, all subjects)   |  |
| 
Predose:
 
 
• Document birth control methods.
 
• Record concomitant medications and review for prohibited or restricted medications.
 
• Record adjustment of current oral antipsychotic, mood stabilizer, or antidepressant therapy.
 
• Assess and record AEs.
 
• Perform a urine pregnancy test (FOCBP only).
 
• Measure weight.
 
• Take vital signs (systolic and diastolic blood pressure, heart rate, and body temperature).
 
• Administer a 12-lead safety ECG in triplicate (5 minutes apart).
 
• Administer the Since Last Visit version of the C-SSRS.
 
• Assess EPS (SAS, AIMS, and BARS).
 
• Administer the PANSS (schizophrenia subjects only).
 
• Administer CGI-S scale, CGI-I scale, and SWN-S (all subjects).
 
• Administer the MADRS, YMRS, and CGI-BP (bipolar subjects only).
 
• Draw a PK blood sample (within 2 hours prior to dosing).
 
• Assessment and confirmation by the investigator that the injection site is appropriate 30 minutes prior to IMP injection.
 
• Have subjects complete a VAS of the level of perceived pain at the injection site completed approximately 30 minutes prior to IMP injection.
 
• Administer IMP.
 
 |  |
| 
Postdose:
 
 
• Have subjects complete a VAS of the level of perceived pain at the injection site approximately 1 hour (± 15 minutes) postdose.
 
• Assessment of the injection site by the investigator completed approximately 1 hour (± 15 minutes) postdose.
 
  |  |

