**Days 176, 183, and 190  $\pm$  2 days (outpatient, subjects receiving aripiprazole 2M LAI 960 mg)**

- Document birth control methods.
- Record concomitant medications and review for prohibited or restricted medications.
- Record adjustment of current oral antipsychotic, mood stabilizer, or antidepressant therapy.
- Assess and record AEs.
- Take vital signs (systolic and diastolic blood pressure, heart rate, and body temperature).
- Administer the Since Last Visit version of the C-SSRS.

Protocol 031-201-00181

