### **3.7.6.5      *Columbia-Suicide Severity Rating Scale***

Suicidality will be monitored during the trial using the C-SSRS. The Baseline/Screening version and the Since Last Visit version of the C-SSRS will be completed by trained trial site staff at the time points presented in the schedule of assessments ([Table 3.7-1](#) for sparse sampling and [Table 3.7-2](#) for robust sampling). This scale consists of a baseline evaluation that assesses the lifetime experience of the subject with suicide events and suicidal ideation and a postbaseline evaluation that focuses on suicidality since the last assessment.

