## 7.6.5 Other Safety Data

### 7.6.5.1 Columbia-Suicide Severity Rating Scale

Suicidality data collected from the C-SSRS assessments will be summarized by treatment group and disease type in incidence of suicidality, suicidal behavior only, emergence of suicidal behavior, suicidal ideation only, emergence of suicidal ideation, emergence of serious suicidal ideation, and worsening of suicidal ideation at each visit and last visit in addition to the overall during the treatment phase.

Descriptive statistics of the incidence of suicidality and incidence of suicidality by type (suicidal behavior and suicidal ideation), as well as the mean changes of Suicidal Ideation Intensity total scores for the most severe ideation from baseline will be reported by visit, treatment group, and disease type.

Protocol 031-201-00181

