## 5.2 Trial Week Windows

The actual assessment date is mapped into the trial week. The definition of trial weeks for primary PK variables are described in [Table 5.2-1](#) and the definitions of trial weeks for efficacy scales and safety scales such as Extrapyramidal Symptoms (EPS) rating scales are included in [Table 5.2-2](#) and [Table 5.2-3](#). Trial days are derived from the formula: Trial Day = Date of assessment - Date of 1st IMP injection + 1. Based on the number of trial days, subjects are mapped to the corresponding trial week. For safety and efficacy variables, only the last observation within the same mapped trial week is used for imputing data on the following trial weeks in the derived last observation carried forward (LOCF) dataset. In addition, only last observations within the same mapped weeks are reported in the summary tables by trial week.

Table 5.2-1 Time Window for Trial Weeks for Primary PK Variables C28 and C56		
Scheduled Visit (Day)	Mapped Week (Trial Week)	Week Window (Trial Day Range ± 2 days)
197	28 (28 days after the 7th injection of 400 mg Abilify Maintena)	195-199
225	32 (28 days after the 8th injection of 400 mg Abilify Maintena or 56 days after the 4 th injection of 960 mg aripiprazole 2M LAI)	223-227

Table 5.2-2 Time Window for Mapping Trial Week for Efficacy Variables		
Scheduled Visit (Day)	Mapped Week (Trial Week)	Week Window (Trial Day Range)
1	Baseline	≤1 (before first IMP)
29	4	2-43
57	8	44-85
113	16	86-141
169	24	142-183
197	28	184-211
225	32	212-239

Protocol 031-201-00181

Table 5.2-3 Time Window for Mapping Trial Week for Safety Variables		
Scheduled Visit (Day)	Mapped Week (Trial Week)	Week Window (Trial Day Range)
1	Baseline	≤1 (before first IMP)
8	1	2-11
15	2	12-18
22	3	19-25
29	4	26-43
57	8	44-71
85	12	72-99
113	16	100-127
141	20	128-155
169	24	156-183
197	28	184-211
225	32	212-239

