### 8.3 Vital Signs

Vital signs include body temperature in supine position, systolic/diastolic blood pressure in supine and standing position and heart rate. Potential clinically relevant vital sign abnormalities will be listed, the criteria for which are provided in [Appendix 1](#).

Incidences of clinically relevant vital signs abnormalities based on observations during scheduled visits and unscheduled post-baseline visits will be tabulated by treatment formulation and disease type. In addition, vital sign parameters and changes from baseline will be summarized by scheduled visit, treatment formulation and disease type.

If vital sign assessments are repeated for the same trial visit, the last repeat values will be used for production of summary tables. This is accomplished by sorting patient data by visit date and visit time (if applicable) within the same trial visit.

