## 8.7 Suicidality

Suicidality data collected from the C-SSRS assessments will be summarized by treatment formulation and disease type in incidence of suicidality; suicidal behavior only, emergence of suicidal behavior; suicidal ideation only, emergence of suicidal ideation, emergence of serious suicidal ideation, and worsening of suicidal ideation at trial visits and last visit in addition to overall during the treatment phase.

Suicidality is defined as reporting any suicidal ideation or behavior. Suicidal behavior only is defined as reporting any type of suicidal behaviors (actual attempt, interrupted attempt, aborted attempt and preparatory acts or behavior) throughout assessment period. Emergence of suicidal behavior is defined as having no suicidal behavior at baseline and reporting any type of behavior at post-baseline. Suicidal ideation only is defined as reporting any type of suicidal ideation. Emergence of suicidal ideation is defined as having no suicidal ideation at baseline and reporting any type of ideation during treatment. Emergence of serious suicidal ideation is defined as having no suicidal ideation at baseline and reporting serious suicidal ideation with score of 4 or 5 on suicidal ideation severity rating during the treatment. In assessment of suicidal ideation and level of severity, each person is given a score of 0 (no ideation present) to 5 (active ideation with plan and intent). Worsening of suicidal ideation is defined as having greater severity of ideation for the most severe suicidal ideation at post baseline than at baseline. Numbers of patients reporting suicidal behavior are also reported by type of suicidal behavior.

Descriptive statistics of the incidence of suicidality and incidence of suicidality by type (suicidal behavior and suicidal ideation), as well as the mean changes of Suicidal Ideation Intensity (SSI) total scores for most severe ideation from baseline will be reported by trial visit, treatment formulation and disease type. The suicidal ideation intensity total score is the sum of suicidal ideation severity rating scores for frequency, duration, controllability, deterrents and reasons for ideation. For each item, each subject gets intensity score from 0 (none) to 5 (worst). Therefore, SSI total score is a range from 0 to 25. If the subject did not endorse any suicidal ideation, a score of 0 is given for the intensity scale.

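### The SAP does not clearly exempt C-SSRS and vital signs from its last-observation-per-week rule; if applied, by-visit C-SSRS rows drop more follow-up on 960 mg and some vital-sign weeks use different days by arm

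*SAP*

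**What the plan says.** SAP 5.2 maps assessment dates to trial weeks. It introduces the windows for efficacy scales and for safety scales, naming EPS as an example, and titles Table 5.2-3 for safety variables generally. Two last-observation rules follow. For LOCF: "For safety and efficacy variables, only the last observation within the same mapped trial week is used for imputing data". For tabulation: "only last observations within the same mapped weeks are reported in the summary tables by trial week".

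The post-baseline rows of Table 5.2-3 are Days 8, 15, 22, 29, 57, 85, 113, 141, 169, 197 and 225. These are the EPS days in both sampling schedules (protocol Tables 3.7-1 and 3.7-2). There is no row for Days 36, 43, 50, 176, 183, 190, 204, 211 or 218, although the sparse schedule takes C-SSRS and vital signs on all of them. In that schedule Days 36, 43 and 50 are for the 960 mg arm only, and so are Days 176, 183 and 190, whose visit heading in protocol Table 3.7.3-2 reads "outpatient, subjects receiving aripiprazole 2M LAI 960 mg".

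The analysis sections use other terms. SAP 8.3: "vital sign parameters and changes from baseline will be summarized by scheduled visit, treatment formulation and disease type". SAP 8.7 reports C-SSRS categories ending with "worsening of suicidal ideation at trial visits and last visit in addition to overall during the treatment phase"; protocol 7.6.5.1 has "worsening of suicidal ideation at each visit and last visit in addition to the overall during the treatment phase". Protocol 3.7.6.5 describes the post-baseline C-SSRS as "a postbaseline evaluation that focuses on suicidality since the last assessment".

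**The concern.** Keeping the last record in a window suits a scale that measures current state and is rated once per window. It does not suit a form that reports only what happened since the previous form, because the last form then says nothing about the earlier part of the window. A sparse 960 mg subject with ideation on the Day 29 form and none on Day 43 would appear at Week 4 without suicidality. The same Day 29 report on 400 mg would be counted, because Day 29 is that arm's only form in the window.

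For vital signs, the same week label would refer to different study days in the two arms wherever one arm has a later visit inside the window.

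Suicidality and vital signs are both primary safety variables (SAP 6.1). As the text stands, two programmers could produce different by-visit tables from it.

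**Working it through.** The documents give no figure to reproduce. I applied Table 5.2-3 to nominal visit days and kept the last record per window.

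**Windows holding more than one C-SSRS form in some arm (SAP Table 5.2-3):** Week 4 = Days 26–43; Week 8 = 44–71; Week 24 = 156–183; Week 28 = 184–211; Week 32 = 212–239.

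**Post-baseline C-SSRS days (protocol Tables 3.7-1, 3.7-2, 3.7.3-2, 3.7.3-3):**
- Sparse 960 mg, 20 forms: 8, 15, 22, 29, 36, 43, 50, 57, 85, 113, 141, 169, 176, 183, 190, 197, 204, 211, 218, 225.
- Sparse 400 mg, 14 forms: the same without 36, 43, 50, 176, 183, 190.
- Robust 960 mg, 16 forms: 22, 29, 36, 43, 50, 57, 85, 113, 141, 169, 190, 197, 204, 211, 218, 225.
- Robust 400 mg, 10 forms by Table 3.7.3-3: 22, 29, 57, 85, 113, 141, 169, 197, 218, 225. Table 3.7-2 has an unqualified mark for 204/211/218, which would add Days 204 and 211 (12 forms).

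**Formula:** days dropped = sum over dropped forms of (day of form − day of previous form). The denominator is 225 − 1 = 224 days.

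| Window | Sparse 960 | Sparse 400 | Robust 960 | Robust 400 (Table 3.7.3-3) | Robust 400 (Table 3.7-2) |
|---|---|---|---|---|---|
| Week 4 | 29, 36: 7+7 = 14 | 0 | 29, 36: 14 | 0 | 0 |
| Week 8 | 50: 7 | 0 | 50: 7 | 0 | 0 |
| Week 24 | 169, 176: 28+7 = 35 | 0 | 0 | 0 | 0 |
| Week 28 | 190, 197, 204: 7+7+7 = 21 | 197, 204: 28+7 = 35 | 190, 197, 204: 21+7+7 = 35 | 0 | 197, 204: 35 |
| Week 32 | 218: 7 | 218: 7 | 218: 7 | 218: 21 | 218: 7 |
| **Days dropped** | **84 (37.5%)** | **42 (18.75%)** | **63 (28.1%)** | **21 (9.4%)** | **42 (18.75%)** |
| Forms dropped | 9 of 20 | 3 of 14 | 7 of 16 | 1 of 10 | 3 of 12 |

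The ratio of 960 mg to 400 mg is 84/42 = 2.0 in sparse and 63/21 = 3.0 or 63/42 = 1.5 in robust. Weighted by planned enrolment (182 sparse, 76 robust):
- 960 mg: (182×84 + 76×63)/258 = 77.8 days.
- 400 mg: (182×42 + 76×21)/258 = 35.8 days, ratio 2.2. On the Table 3.7-2 reading it is 42 days, ratio 1.9.

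Drawing each sparse visit uniformly within its ±2-day window gives about 86 against 43 days, so the result does not depend on exact attendance, although Days 43, 183 and 211 are the last days of their windows.

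**Vital signs, if the same rule is applied:**
- Week 4: Day 43 on 960 mg, Day 29 on 400 mg, in both schedules (14 days apart).
- Week 24, sparse: Day 183 on 960 mg, Day 169 on 400 mg (14 days apart). Robust: Day 183 in both arms.
- Weeks 8, 28 and 32: Days 57, 211 and 225 in both arms.

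**EPS:** one rating per window in both arms, so nothing is dropped.

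**The case against.** The strongest reply is that the rule was never meant for these variables. Its tabulation sentence concerns tables by trial week. The SAP uses that term for EPS (8.8) and refers to mapped trial weeks for efficacy (9), while 8.3 speaks of scheduled visits and 8.7 of trial visits. Table 5.2-3 matches the EPS days exactly. SAP 8.3 has its own rule for repeats within a visit, which the window rule would make redundant. The protocol's schedules already define every visit, and protocol 7.6.3 and 7.6.5.1 call for results at each visit.

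This shows that the scope is uncertain, most of all for vital signs, but it does not settle it. The table is titled for safety variables and has its own scheduled-visit column. EPS is given only as an example. SAP 8.5 uses mapped trial visit and trial visit for the same thing. The repeat rule in 8.3 sorts by date as well as time, which matters only if one visit can span several dates.

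The second reply is that little is lost, and most of this stands. C-SSRS is also summarised overall, C-CASA categories and suicidality-related adverse events are tabulated (8.7, 8.10), and vital-sign abnormality incidence uses all scheduled and unscheduled post-baseline visits (8.3). No test rests on the by-visit rows. One gap remains: 8.7 does not say that the overall row uses every form. Under the COVID-19 arrangements in SAP 7.5, vital signs are not among the examples of remote assessments at sparse between-dose visits, so that mismatch may be smaller in practice; C-SSRS is listed.

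Thirdly, taking the worst form per window does not equalise the arms. In the sparse schedule Week 4 would cover 21 days on 960 mg (Day 22 to 43) and 7 on 400 mg (Day 22 to 29), and Week 24 would cover 42 against 28. That stands as a limitation, but no report would disappear.

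**Conclusion.** The SAP leaves open whether the last-observation rule governs C-SSRS and vital signs. If it does, it is the wrong rule for C-SSRS by-visit rows: on nominal days it drops about twice as much follow-up on 960 mg as on 400 mg overall (ratio 1.9 to 2.2), with 2.0 in sparse and 1.5 or 3.0 in robust. For by-visit vital signs it would put different days under Week 4 in both schedules and under Week 24 in the sparse schedule. The figures assume full follow-up to Day 225 and no unscheduled C-SSRS forms.

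Three stronger readings are tempting and are not supported. A reader might infer that the safety evaluation as a whole is biased towards the test product; only by-visit rows are exposed, and the overall, C-CASA, adverse-event and abnormality tables remain. A reader might object that mid-interval vital signs on 960 mg would be set against end-of-interval values on 400 mg; this comes from the 56- and 28-day dosing intervals and would remain with Day 29 in both arms. A reader might also extend the Week 24 mismatch to the robust schedule, where both arms have vital signs on Day 183.

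**What to change.** In SAP 5.2, 8.3 and 8.7, limit the last-observation rule to EPS and efficacy scales, and then state:
- **C-SSRS:** tabulate at each protocol visit. If windows are kept, report the most severe result across all forms in the window and show the number of days covered in each arm. Build the overall row from all post-baseline forms.
- **Vital signs:** use the record nearest the scheduled day in Table 5.2-3, and show the 960 mg-only visits as separate rows.

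The protocol should also reconcile Tables 3.7-2 and 3.7.3-3 on whether robust 400 mg subjects complete the C-SSRS on Days 204 and 211.

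The cost is SAP wording and a small programming change, with no new data. The tables become longer, and windowed C-SSRS rows would still differ in length between arms, which is why the days covered should be shown.

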### 5.3 Handling of Missing Data

No data imputation is done for missing data in the PK analysis. The last observation carried forward (LOCF) method is used to impute missing data of the safety EPS assessment scales and efficacy assessment scales at postbaseline visits. The observed case (OC) dataset corresponding to a visit consists of data from all subjects who are evaluated at that visit. In the LOCF dataset, missing data at a postbaseline visit are imputed with the value obtained at the nearest preceding visit, except that baseline values are not carried forward to impute missing values at a postbaseline visit. In addition, the Mixed effect Model Repeated Measure (MMRM) for selected efficacy endpoints are explored to address the potentially informational missing (refer to [Section 9](#)).

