### **3.8.3 Individual Subject Discontinuation**

#### **3.8.3.1 Treatment Discontinuation**

After the first dose of IMP, a subject may discontinue from the trial for a variety of reasons. Treatment discontinuations may be initiated by a subject or may become medically necessary due to AEs, required treatment with a disallowed medication or therapy, or other reasons, as determined by the investigator. If a subject discontinues treatment, their participation in the trial will be discontinued. Discontinued subjects should be encouraged to complete all ET and follow-up assessments with ET assessments conducted as soon as possible after the subject is withdrawn.

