#### **3.8.3.2 Documenting Reasons for Discontinuation**

All subjects have the right to withdraw and the investigator can discontinue a subject's participation in the trial at any time if medically necessary. In addition, subjects meeting the following criteria must be withdrawn from the trial (only one reason for discontinuation [the main reason] can be recorded in the eCRF):

- Death

Protocol 031-201-00181

- Disease relapse or disease progression
- Failure to meet randomization criteria
- Lost to follow-up
- Non-compliance with IMP (if confirmed not related to an AE)
- Physician decision (other than AE)
- Pregnancy (see [Section 5.5](#))
- Site terminated by sponsor
- Trial terminated by sponsor
- Withdrawal of consent by parent/guardian (if confirmed not related to an AE)
- Withdrawal of consent by subject (if confirmed not related to an AE)

If the subject discontinues IMP due to an AE, the investigator, or other trial personnel, will make every effort to follow the event until it has resolved or stabilized. Follow-up procedures in [Section 3.8.3.1](#) must be followed. Subjects may be replaced, if discontinuations/withdrawals occur, as described in [Section 3.3](#).

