In addition, the linear mixed-effects mode will be used to explore the effect of the treatment and change from baseline over the time for efficacy endpoints, i.e. SWN-S total score, PANSS total score and YMRS total score. Change from baseline in those efficacy endpoints will be analyzed using MMRM analysis with a restricted maximum likelihood (REML) approach. Analyses will include the categorically fixed effects of treatment, disease type (if applicable), PK sample scheduling (if applicable), trial week, and treatment-by trial week interaction, as well as the covariates of baseline-score-by-week interaction in addition to subject as random effect. An unstructured covariance structure will be used to model the within-subject errors and Kenward-Rodger degree of freedom will be used to test the fixed effects. If this analysis approach fails to converge, the covariance structures of heterogeneous compound symmetry will be utilized in the analysis and the “sandwich” estimator of the variance covariance matrix of the fixed effects parameters will be used in order to deal with possible model misspecification of the covariance matrix. 95% confidence intervals (CIs) for difference of changes from baseline in efficacy endpoints or values of efficacy endpoints between aripiprazole 2M LAI 960mg and IM depot 400 mg will be provided at trail weeks as well.

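### SAP 5.3 credits an exploratory MMRM with addressing informative missing data, but the model assumes missing at random, so efficacy differences can be biased if relapse or early-termination ratings differ by arm

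*SAP*

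**What the plan says.** SAP 5.3 uses LOCF for the efficacy scales, with an observed-case (OC) dataset beside it. It then adds that "Mixed effect Model Repeated Measure (MMRM) for selected efficacy endpoints are explored to address the potentially informational missing".

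SAP 9 gives the model: "Change from baseline in those efficacy endpoints will be analyzed using MMRM analysis with a restricted maximum likelihood (REML) approach", with an unstructured covariance, for "SWN-S total score, PANSS total score and YMRS total score". Its output includes "95% confidence intervals (CIs) for difference of changes from baseline in efficacy endpoints" at the trial weeks. No efficacy hypothesis test, margin or alpha is set.

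Protocol 3.8.3.2 says that "subjects meeting the following criteria must be withdrawn from the trial", and the list includes "Disease relapse or disease progression". Protocol 3.8.3.1 adds: "If a subject discontinues treatment, their participation in the trial will be discontinued". On the last rating it says only that "Discontinued subjects should be encouraged to complete all ET and follow-up assessments".

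The Day 225/ET visit lists the efficacy scales (Protocol Tables 3.7.3-2 and 3.7.3-3). SAP Table 5.2-2 assigns every assessment from Day 2 to Day 239 to an analysis week. SAP 4 assumes 34% dropout, not split by arm or reason. SAP 2.2 makes efficacy a secondary objective, aimed at obtaining information.

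The readable SAP states no missing-at-random assumption and contains no sensitivity analysis for data missing not at random. Text after SAP 10.2 and in the appendices is redacted, so this absence is stated for the readable text only.

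**The concern.** A likelihood MMRM predicts a subject's unseen visits from that subject's observed scores and from subjects with similar histories who stayed. This is valid if, given the observed scores, leaving tells nothing more about the unseen ones. Informative missingness is the case where that fails. SAP 5.3 therefore credits the model with a property it does not have.

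This matters because one route out of the trial is tied to the outcome. A relapsing subject must leave, no later visits are rated, and the rating that would show the relapse may not be taken. If relapse or ET capture differs between the regimens, the reported difference and its interval can be off while the SAP describes the method as dealing with informative dropout.

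**Working it through.** **The plan's own figure.** Enrolment = completers / (1 - dropout). 100/0.66 = 151.5, so 152; 170/0.66 = 257.6, so 258. Both match SAP 4. No figure in the documents is attached to the MMRM statement, so the sizes below rest on assumptions. Two models of relapse were used, because the trial data cannot show which is closer to the truth.

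**Model A: withdrawal when a score crosses a threshold, with later scores following the same normal distribution.** Assumed: 129 per arm, six post-baseline visits, score SD 12, correlation 0.6, about 25% to 40% missing at Week 32, 1,500 runs, test arm worse by the true difference. Bias in the MMRM difference at Week 32, in points (Monte Carlo SE about 0.04):

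| Relapse score recorded | True 0 | True 3 | True 6 |
|---|---|---|---|
| Always | +0.1 | -0.1 | +0.1 |
| Half the time | 0.0 | -0.2 | -0.6 |
| Never | +0.1 | -0.5 | -1.1 |
| Reference arm only | -1.8 | -2.3 | not run |

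When the score is always recorded, withdrawal depends on observed data and MMRM is essentially unbiased. When it is never recorded, the reference-arm mean looks too good by about 2 points, although the arm difference is unbiased if there is no true difference. At true difference 6 with no score recorded, the bias is -2.1 for OC and -1.9 for LOCF. With capture in the reference arm only, LOCF bias is -5.3 and -6.2 (true 0 and 3).

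**Model B: relapse as a lasting change of state.** Assumed:
- relapse by Week 32 of 16% v 8%, at times uniform over 32 weeks;
- a sustained PANSS rise of 15 or 25 points;
- random intercept SD 7 or 6 with residual SD 6 or 7. The correlation is 49/85 = 0.58 or 36/85 = 0.42;
- 25% other dropout at random;
- 200,000 subjects per arm.

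Total loss is 1 - 0.84 x 0.75 = 37% and 1 - 0.92 x 0.75 = 31%, averaging the plan's 34%. The true Week 32 difference is (0.16 - 0.08) x 15 = 1.2 or x 25 = 2.0 points.

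| ET ratings obtained | Share recovered by MMRM | Share recovered by LOCF |
|---|---|---|
| All | 0.32 to 0.44 | about 0.88 |
| None | about 0 | about 0 |

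The MMRM range covers runs that differ in implementation detail. MMRM loses much of the difference even with full ET capture because no post-relapse course is seen in either arm, so later visits are predicted from subjects who did not relapse. The LOCF figure has a simple check: if other dropout is also spread evenly over time, a relapser has already left for another reason with probability 0.25/2 = 0.125, and 1 - 0.125 = 0.875.

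**Equal relapse, 12% v 12%, in Model B.** With equal ET capture the MMRM bias is about 0, whether ratings are obtained or missed. With ET ratings captured in one arm only, MMRM shows a difference of 0.6 to 1.0 points where none exists.

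**The case against.** The case against is substantial, and most of it stands.

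- MMRM is not the plan's main defence. It is explored for three scales, alongside LOCF and OC summaries. A reader might infer that the plan relies on it; the text does not say so.
- A reader might infer that forced withdrawal on relapse by itself leaves the comparison biased. It does not. Withdrawal after a recorded worsening can be missing at random; the ET visit and the continuous analysis windows are there to bring that score into the model. Deterioration need not end participation either, since Protocol 3.2.4 allows a previous oral non-aripiprazole antipsychotic to be resumed after Day 28.
- A reader might also infer that the bias always runs toward no difference. Unequal ET capture can create a difference where there is none.
- The 16% v 8% contrast has no support in the documents. Protocol 2.2 expects comparable or slightly higher exposure on the test product.
- The assumed differences are small beside the precision. With total SD sqrt(85) = 9.2 and 85 completers per arm, the 95% half-width is 1.96 x 9.2 x sqrt(2/85) = 2.8 points. With an SD of about 7.5 after baseline adjustment it is 2.3. It is wider for PANSS, which only schizophrenia subjects have.
- SAP 7.1 already tabulates discontinuation reasons by formulation, so an imbalance in relapse would show.

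Two things remain. The sentence in SAP 5.3 is incorrect as a statement about the method. The LOCF and OC summaries also do not cover the case where ET ratings are missed: under Model B, LOCF then recovers about none of the difference.

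**Conclusion.** The point holds in a limited form. As specified, the MMRM assumes missing at random and does not address informative missingness. The readable SAP has no analysis that does. The arm differences and 95% CIs for the three scales can be biased if relapse rates or ET-rating capture differ by arm.

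The documents give neither quantity, so size and direction cannot be stated for this trial. The results run from essentially no bias (equal relapse and equal capture, or a recorded score under Model A) to loss of nearly all of an assumed 1.2 to 2.0 point difference, or a spurious 0.6 to 1.0 points. These figures depend on the assumed relapse rates, score rise, SDs and correlations, and show order of magnitude only.

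The consequence is confined to a secondary, informational objective with no test or margin. A finding that the efficacy results are biased, or biased toward similarity, would go beyond the documents.

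**What to change.** 1. In SAP 5.3 and 9, state that the MMRM assumes missing at random, and delete the statement that it addresses informative missingness.
2. Add one delta-adjusted multiple-imputation sensitivity analysis for the SWN-S, PANSS and YMRS totals. After withdrawal for relapse, AE or physician decision, shift the imputed scores in the worse direction (up for PANSS and YMRS, down for SWN-S) in prespecified steps, separately by arm. Report the estimated arm difference and 95% CI at each step. A tipping point is not suitable, because without an efficacy test or margin there is no conclusion to tip.
3. Extend the discontinuation table in SAP 7.1 to show, by reason and arm, how many withdrawn subjects have ET scores on these scales.

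The cost is a few lines of SAP text, one standard analysis on three endpoints and one table. No new data are needed. The downside is a little more work, and efficacy may look less favourable.
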